6. *Self-Regulation Mechanisms Hypotheses:* In 4 different fMRI tasks, we hypothesize (a) greater activation of anterior cingulate cortex (ACC) and medial orbitofrontal cortex (OFC) and decreased activation in amygdala/hippocampus after MTPC intervention compared to before intervention (i.e. a pre-post increase) in an emotional Go/NoGo inhibitory control task; (b) greater activation of insula after (compared to before) MTPC in a self-compassion task (that contrasts self-reassurance conditions with a self-criticism condition); (c) greater insula activation during an interoceptive attention task (that contrasts an interoceptive attention condition with an exteroceptive attention condition); and (d) greater rostral ACC (rACC) and ventromedial prefrontal cortex (vmPFC) activation during the anticipation of pain and greater activation in the lateral prefrontal cortex (LPFC) and somatosensory areas during pain in an emotion/pain regulation task, after compared to before the MTPC intervention.
We hypothesize that all inhibitory control and interoceptive targets will be associated with higher levels of initiation of regimen adherence, while self-compassion, interoceptive targets and emotion/pain regulation will be associated with higher levels of regimen maintenance.

HEART Pilot Study Hypotheses

7. ***HEART pilot study validation goal:*** Our goal is to implement activity and heart-rate tracking, nutrition, sleep, and mindfulness practice tracking in a cohort of MINDFUL-PC alumni to determine whether this suite of behavioral monitoring tasks can behaviorally validate the signal from the self-reported action plan initiation protocol.

We hypothesize that self-reported action plan initiation with activity, diet, sleep or mindfulness practice will be associated with a behavioral change as assessed with the daily tracking devices.

8. ***HEART pilot study concurrent cohort:*** We hypothesize that participants who are in an 8-week MTPC group will demonstrate higher levels of action plan initiation, with an associated change in behavioral monitoring, than participants who are randomized to the waitlist condition. We also hypothesize that participants who chose to increase activity will have a greater increase in daily activity than those who chose a diet-, mindfulness- or sleep-related action plan goal.

B. Background and Rationale:

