Using an intent-to-treat analysis, we will use logistic regression and Mixed Effects Modeling to evaluate for main effects of MTPC, mindfulness-trained PCPS, and the interaction of the two on binary and continuous ratings of level of action plan initiation and maintenance. We will conduct exploratory linear regression models of post-study mindfulness and self-compassion and overall practice dose as independent variables with level of action plan initiation and maintenance as dependent variables.

The experimental fMRI pilot analyses methods are described below.

6. *Self-Regulation Mechanisms Hypotheses*: In 4 different fMRI tasks, we hypothesize (a) greater activation of ACC and OFC and decreased activation in the amygdala/hippocampus after MTPC intervention compared to before intervention (i.e. a pre/post increase) in an emotional Go/NoGo inhibitory control task, as in Perez 2016 [69], using validated emotional pictures (International Affective Pictures System, IAPS, [70]). The task includes 448 IAPS pictures (50% neutral and 50% unpleasant), which will

be presented briefly (1.5 seconds), while participants either react (Go) or withhold a button press reaction (NoGo), depending on abstract symbols presented on top of the pictures; (b) greater activation of mid-posterior insula after (compared to before) MTPC in a self-compassion task (that contrasts a self-reassurance condition with a self-criticism condition), as in Longe 2010 [71]; (c) greater insula activation during an interoceptive attention task (that contrasts an interoceptive attention condition with an exteroceptive attention condition) as in Farb 2013[72], and d) increases in the rostral ACC (rACC) and ventromedial prefrontal cortex (vmPFC) during the **anticipation of pain** after compared to before MTPC and increased activation in the lateral prefrontal cortex (LPFC) and somatosensory areas **during pain** after compared to before the MTPC, as in Kim 2013 [73]. We hypothesize that all inhibitory control and interoceptive targets will be associated with higher levels of initiation of regimen adherence, while self-compassion, emotion/pain regulation, and interoceptive targets will be associated with higher levels of regimen maintenance.

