We will follow current recommended methods for fMRI data analysis [74,75], especially in the case of longitudinal data [76-82]. Our approach is based on a priori regions-of-interest (ROI), a method more statistically powerful than whole-brain analyses since it limits the number of statistical tests to the voxels included in the ROI and thereby reduces Type I errors [83, 84]. Another advantage of using a ROI-based approach is that it enables precise spatial correspondence of the region of interest across subjects, since it does not involve normalizing different brains to a common atlas [87]. In this study, our ROIs are the following: OFC and amygdala/hippocampus (in the emotional Go/NoGo task), the mid-to-posterior section of the insula (in the self-compassion task, and emotion/pain regulation task), the anterior insula (in the interoceptive attention task) the DLPFC and rACC/vmPFC in the emotion/pain regulation task and Go/NoGo task.

The fMRI data will be analyzed using the following standard software packages: FSL [85, 86], FreeSurfer [87-90], AFNI [91, 92], and RETROICOR [93] for retrospective correction of physiological motion artifacts using our peripheral measures of cardiac and respiratory activity as independent assessments of physiological noise in the blood oxygen level-dependent (BOLD) signal. Following standard preprocessing steps (de-warping, slice timing correction, motion correction, removal of physiological noise signals), the statistical analysis of brain activation data will be performed using a linear mixed effects (LME) model, following recent recommendations for longitudinal fMRI analysis [76, 79, 80]. This approach is implemented in the AFNI software package with the group analysis program 3dLME [80]. This program will be used to solve the LME system (via built-in optimization procedures) and test our hypotheses. Of note, the LME approach is more general than the commonly-used General Linear Model (GLM), AN(C)OVA, regression, and t-tests, while including those as special cases. The LME approach is recommended for longitudinal fMRI data analysis because it includes in the model the covariance structure of serial measurements performed in the same subject, whereas the commonly-used GLM model assumes that there is no such correlation, which is incorrect in the case of longitudinal data [80]. In addition, the LME framework can offer superior statistical power in detecting longitudinal group differences [79, 80].

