Self-Regulation hypothesis testing for the fMRI data will be performed as follows. For each of the 4 fMRI tasks, we will use a Linear Mixed Effects model of the BOLD signal in the ROIs associated with that task (described above), with 2 time points (pre- and post-intervention). The

model will include the following regressors of interest: gender, age, and the following pre-intervention scores: depression (PROMIS-DSF), anxiety (PROMIS-ASF), self-compassion (SCS-SF), and mindfulness (FFMQ); and the following regressors of no interest: head motion parameters and cardiac and respiratory components of physiological noise. Hypothesis will be expressed as: Is there any significant difference between the 2 time points in the task-specific ROI activation during a) NoGo trials versus Go trials, b) self-reassurance versus self-criticism, c) Interoception-versus-Exteroception, and d) expectation of pain and pain versus rest. The null hypothesis will be that the ROI activation at the 2 time points are not significantly different. Significance testing will be done using permutation/bootstrapping methods (see [79, 80]).

1. HEART pilot study analysis plan: The HEART pilot study aims to recruit 40 participants in the **alumni cohort** and 30 participants (10-20 in the waitlist arm and 20-40 in the intervention arm) in the **concurrent cohort** for a total of 70 participants. The data would be examined for correlations between the action plan initiation 7-item survey and pre-post differences in step count, the number of active periods, changes in sleep duration, changes in mindfulness practice, and change in nutritional habits depending on which action plan goal was specified in the patient action plan. We will also examine the percentage of action plan initiation events ≥ 5 on the APIS-5 that have a corresponding behavioral change evidenced in the daily data collection. Finally, we will also examine whether the activity changes are greater in the participants who selected exercise as compared to those who selected nutrition or dietary changes and vice versa.

C.5.c. Sample Size calculations:

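### The somatosensory part of fMRI hypothesis 6(d) has no region of interest and so no planned pre/post test; the region list and pain contrast should be aligned with the hypotheses by task and phase

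*Combined protocol and SAP*

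**What the plan says.** The fMRI hypotheses appear twice, in A.2.b item 6 and in C.5.b item 6. For the pain task both versions predict by phase. During anticipation the predicted regions are rACC and vmPFC. During pain, A.2.b gives "greater activation in the lateral prefrontal cortex (LPFC) and somatosensory areas during pain in an emotion/pain regulation task", and C.5.b repeats the same two regions. For the other tasks C.5.b predicts "greater activation of ACC and OFC and decreased activation in the amygdala/hippocampus after MTPC intervention" (emotional Go/NoGo), "greater activation of mid-posterior insula after (compared to before) MTPC in a self-compassion task", and "greater insula activation during an interoceptive attention task".

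The next paragraph of C.5.b chooses an ROI approach over whole-brain analysis, partly because it limits the number of tests, and then lists the ROIs. Go/NoGo gets OFC and amygdala/hippocampus. Two tasks share "the mid-to-posterior section of the insula (in the self-compassion task, and emotion/pain regulation task". The interoceptive task gets the anterior insula. Last come "the DLPFC and rACC/vmPFC in the emotion/pain regulation task and Go/NoGo task".

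The hypothesis-testing paragraph of C.5.b fits a linear mixed effects model, for each task, in the ROIs already listed for that task, with two time points. Its contrast for the pain task is "d) expectation of pain and pain versus rest".

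**The concern.** An a priori ROI analysis tests only what its list contains. If a predicted region is not listed, the prediction cannot be confirmed or refuted by following the plan. If a region is listed without a prediction, a positive result there can later be presented with the same standing as a hypothesised one. If regions are predicted for one phase of a task but neither list nor contrast is tied to a phase, the analyst has a free choice of which phase counts as the test.

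D.4.c says the pilot is meant to give effect sizes for the fMRI and adherence measures, to power the next phase. C.5.b item 6 also expects emotion/pain regulation targets to relate to maintenance of the regimen. A predicted target with no planned measurement leaves a gap in both uses.

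**Working it through.** The plan gives no figure on this point, so the check sets the predictions beside the ROI list.

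**Inputs.** Predictions: A.2.b item 6 and C.5.b item 6. ROI list: the fMRI methods paragraph of C.5.b. Restriction and contrasts: the hypothesis-testing paragraph of C.5.b.

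**Matching rule.** Lenient, in the plan's favour. rACC/vmPFC in Go/NoGo counts as covering ACC (its vmPFC part can also be read as overlapping the medial OFC named in A.2.b). DLPFC in the pain task counts as covering LPFC. Anterior insula counts as covering insula. In the pain task rACC and vmPFC count as one entry.

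| Task | Predicted | Listed ROIs | Predicted, not listed | Listed, not predicted |
|---|---|---|---|---|
| Emotional Go/NoGo | ACC; OFC; amygdala/hippocampus | OFC; amygdala/hippocampus; rACC/vmPFC; DLPFC | none | DLPFC |
| Self-compassion | mid-posterior insula | mid-to-posterior insula | none | none |
| Interoceptive attention | insula | anterior insula | none | none |
| Emotion/pain regulation | rACC/vmPFC (anticipation); LPFC (pain); somatosensory areas (pain) | rACC/vmPFC; DLPFC; mid-to-posterior insula | somatosensory areas | mid-to-posterior insula |

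**Counts.**
- Predicted pairs: 3 + 1 + 1 + 3 = 8.
- Listed pairs: 4 + 1 + 1 + 3 = 9.
- Matched pairs: 3 + 1 + 1 + 2 = 7.
- Predicted without an ROI: 8 − 7 = 1.
- Listed without a prediction: 9 − 7 = 2.

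Counting rACC and vmPFC separately, the pain task has four predicted regions and one of them has no ROI.

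**Is there another route to a test?** No whole-brain analysis is planned. D.1.a says adherence results will be correlated with activation in the hypothesised regions. That could be read to include somatosensory areas, but it defines no ROI and no model, and a correlation with adherence is not the pre/post comparison that 6(d) predicts.

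**Phases.** The predictions for anticipation and for pain differ by region, not by direction; all are increases. The contrast names both phases in one item against rest. It can mean one combined contrast or two contrasts that share a baseline. Neither that item nor the ROI list says which region is tested in which phase.

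**The case against.** **The extra regions are pre-specified.** DLPFC in Go/NoGo and insula in the pain task are named before analysis, and the planned test is non-directional, so each can be tested validly without a stated direction. The DLPFC pairing may also be a by-product of one compressed phrase that joins two regions to two tasks and is needed to give Go/NoGo its cingulate region. Both points stand. What remains is that the hypotheses say nothing about these two pairs, so the plan should state their standing.

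**Hypothesis 6(d) as a whole.** A reader might infer that 6(d) cannot be tested at all. The documents do not support that: rACC/vmPFC is listed, and LPFC is covered if DLPFC is accepted for it. One regional component is untested.

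**The pain contrast.** A reader might infer that the plan averages anticipation and pain, so that an effect present in one phase only would be diluted. The documents do not support that either. No text says the phases are pooled, C.5.b item 6 separates them explicitly, and the wording reads just as well as two comparisons with rest. No loss of signal or power can therefore be attributed to the plan. What stands is the ambiguity and the missing link between region and phase.

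**Importance.** This is an optional, within-subject pilot. D.4.c speaks generally of effect sizes for the next phase and does not say that somatosensory activation will drive that calculation. This limits the severity, but the omission remains.

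**Conclusion.** The somatosensory omission is wrong as written: a prediction stated in both A.2.b and C.5.b has no ROI, and the testing paragraph confines the models to the listed ROIs. The size is 1 of 8 predicted task-region pairs without a planned pre/post test, and 2 of 9 listed pairs without a prediction. These counts rest on the lenient matching above; a literal reading of the region names would add mismatches (LPFC against DLPFC, ACC against rACC/vmPFC, insula against anterior insula).

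The pain contrast is an ambiguity to be resolved, not an error with a measurable cost. Severity is minor. The scope is the fMRI pilot of at most 30 patients; the randomised comparison of MTPC with control is unaffected.

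**What to change.** In the ROI paragraph of C.5.b, add a somatosensory ROI for the pain phase. If the investigators prefer, they can instead drop that prediction from A.2.b item 6 and C.5.b item 6; either restores consistency. In the same paragraph, label DLPFC in Go/NoGo and mid-to-posterior insula in the pain task as exploratory.

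In the hypothesis-testing paragraph of C.5.b, replace the single pain item with two contrasts: anticipation versus rest, tested in rACC/vmPFC, and pain versus rest, tested in LPFC/DLPFC and, if kept, the somatosensory ROI.

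The cost is a few sentences of analysis text and, if the ROI is added, one more ROI test. No new scanning is needed.

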The **Perceived Control Questionnaire (PCQ)** is adapted from a 5-item perceived control measure from Jerant et al. [55] and a previously validated survey from Armitage et al. [56]. This 5-item scale ask participants to rate their sense of control over chronic illness self-management on a 7-point scale from 1 (*None*) to 7 (*Total*). Items include "How much personal control do you have over your self-management behaviors?" Duration: 3 min.

Action Plan Worksheet/SMART Goal Video: Patient participants will complete the Action Plan Worksheet and watch a brief video about creating SMART goals (for example, <https://www.youtube.com/watch?v=1-SvuFIQjK8>) in PT Study Week 7. The Action Plan Worksheet is a 13-item worksheet that incorporates information about SMART goals to support patient participants to make a goal about their health in one of 3 categories (activity level/exercise, diet/eating/drinking, or mindfulness meditation practice). Patients are encouraged to share this worksheet with a person who may help the patient in accomplishing the goal, and/or a healthcare provider. Duration: 15 min.

Patients will complete the self-report **Action Plan Assessment (APA-10)** questionnaire after filling out the Action Plan Worksheet, at PT Study Week 7. This survey instrument is developed as an adaptation of two self-determination theory scales [57] [58] and incorporates elements of shared decision-making [59] and self-efficacy and barrier appraisal [60]. This 10-item scale evaluates patient behavior in the domains of self-determination, motivation, shared decision-making, and barrier appraisal. Participants are asked to rate their agreement with a statement on

a 7-point scale from 1 (*Strongly Disagree*) to 7 (*Strongly Agree*). A sample item includes “I have agreed to this action plan because I want to do it for myself.” Duration: 5 minutes.

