Patient self-reported **Action Plan Initiation Survey (APIS-5)** will be administered at post-treatment (PT Study Week 8, 12, and 16). This 5-item questionnaire is adapted from a measure used by Guck et al. [56]. In this questionnaire, patients are asked to list their action plan goals generated with their PCP, and determine whether they met or did not meet each goal. Patients are asked to categorize their goals into one of six categories: diet/eating/drinking, exercise/activity, sleep, medication, reducing substance use, and self-care. For each unmet goal, patients are asked to rate the cause of not meeting the goal on an attributional rating scale using a 7-point format. Higher scores indicate internal rather than external and uncontrollable rather than controllable attributions. A sample item includes: “Was the cause of not meeting this goal controllable by you?” where 1 is “Extremely controllable” and 7 is “Not at all controllable.” Duration: 5 minutes. Participants in the HEART pilot study in the concurrent cohort will fill this out as per the main study timeline. Participants in the HEART pilot study alumni cohort will fill this out at the end of HEART study Weeks 4 and 5.

The **Three-Factor Eating Questionnaire-R18 (TFEQ-R18)** is an 18 item questionnaire that refers to current dietary practice and measures 3 different aspects of eating behavior: restrained eating (conscious restriction of food intake in order to control body weight or to promote weight loss), uncontrolled eating (tendency to eat more than usual due to a loss of control over intake accompanied by subjective feelings of hunger), and emotional eating (inability to resist emotional cues). The TFEQ-R18 consists of 18 items on a 4-point response scale (definitely true/mostly true/mostly false/definitely false). Responses to each of the 18 items are given a score between 1 and 4 and item scores are summated into scale scores for cognitive restraint, uncontrolled eating, and emotional eating. An example item includes “Sometimes when I start eating, I just can’t seem to stop.” Duration: 5 minutes.

C.3.f.7. HEART Pilot Study Battery:

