The HEART pilot study aims to recruit 40 participants in the **alumni cohort** and 30-60 participants (10-20 in the waitlist arm and 20-40 in the intervention arm) in the **concurrent cohort** for a total of 70 participants (40 alumni, 20 intervention, and 10 waitlist). The absolute minimum total number would be 47 participants and the maximum total would be 100 participants (40 alumni, 40 intervention, and 20 waitlist).

D.4. Data Quality and Safety:

D.4.a. Data Quality and Management:

D.4.a.1. Description of Plan for Data Quality and Management:

The PI and data manager will review data collection, data completeness and accuracy as well as protocol compliance on a monthly basis.

Survey session data will be entered by subjects into REDCap. The data manager will review all REDCap data collection forms on an ongoing basis for data completeness and accuracy as well as protocol compliance.

All scantron data will be scanned by research coordinators and files will be reviewed by the data manager for completeness and accuracy prior to upload to the excel database.

Any surveys completed by pencil and paper will be entered by a research assistant. We will conduct ongoing verification audits for entry of any data transfer from paper forms. Discrepancies will be corrected by data manager and/or the PI, based on source documents. Any inconsistencies will be resolved. Exploratory analysis of data with simple range checks may be conducted periodically as a second audit of possible entry errors.

Frequency of Review—**The frequency of data review for this study differs according to the type of data and can be summarized in the following Data Quality Monitoring Table.**

Table 5. MTPC Data Quality Monitoring Table

Data type	Frequency of review	Reviewer
Study progress and safety	Monthly	Program Manager, PI
Data collection, data quality/completeness/accuracy, protocol compliance	Monthly	Data Manager, PI
Subject accrual (including compliance with protocol enrollment criteria)	Quarterly	PI, Independent Monitor
Status of all enrolled subjects, as of date of reporting	Quarterly	PI, Independent Monitor
Adherence data regarding study visits and intervention	Quarterly	PI, Independent Monitor

Data type	Frequency of review	Reviewer
AEs	Quarterly	PI, Independent Monitor
Protocol violations	Per occurrence	PI, Independent Monitor, NCCIH
SAEs	Per occurrence	PI, Independent Monitor, NCCIH

D.4.b. Subject Accrual and Compliance:

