The HEART pilot study is underpowered to be able to compare between-group differences in outcomes, but the primary aims of the pilot study are 1) to demonstrate feasibility of using

commercially available activity/sleep/diet trackers and online daily surveys for ecological behavior tracking in a MBI RCT and 2) to use the daily behavior tracking to validate the action plan goal setting process and the self-report action plan initiation measure. To do this we aim to recruit the 70 participants from both the alumni and concurrent phases and then to examine the data for correlations between the action plan initiation 7-item survey and pre-post differences in step count, the number of active periods, changes in sleep duration, changes in mindfulness practice, and change in nutritional habits depending on which action plan goal was specified in the patient action plan. When conducting correlation analysis with 70 participants, using $\alpha = 0.05$ type 1 error rate, we would have 80% to find a correlation coefficient of 0.33. If we have lower than expected recruitment and only had 47 participants for correlation analysis, using $\alpha = 0.05$ type 1 error rate, we would have 80% to find a correlation coefficient of 0.4, which represents moderate correlation⁹⁶. We will also examine whether the activity changes are greater in the participants who select exercise as compared to those who selected nutrition or dietary changes and vice versa.

D.4.d. Stopping Rules:

This study will be stopped prior to its completion if: (1) the intervention is associated with adverse effects that call into question the safety of the intervention; (2) difficulty in study recruitment or retention will significantly impact the ability to evaluate the study endpoints; (3) any new information becomes available during the trial that necessitates stopping the trial; or (4) other situations occur that might warrant stopping the trial.

D.4.e. Designation of an Independent Monitor:

The Independent Monitor for this study is [name], MD at Boston Medical Center. [name] is not associated with this research project and thus works independently of the PI, [name]. [name] is not a part of the key personnel involved in this grant, and is qualified to review the patient safety data generated by this study because of her unique expertise in the area of mindfulness training for primary care patients.

D.4.f. Safety Review Plan:

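### HEART pilot: hypothesis 8 compares activity goals with diet, mindfulness and sleep goals, but the planned contrast compares them with diet goals only

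*Combined protocol and SAP*

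**What the plan says.** Section A.2.b, hypothesis 8, is headed for the HEART concurrent cohort. Its second sentence predicts that participants who chose to increase activity will show a "greater increase in daily activity than those who chose a diet-, mindfulness- or sleep-related action plan goal".

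Section C.5.b (HEART analysis plan) says the study will examine "whether the activity changes are greater in the participants who selected exercise as compared to those who selected nutrition or dietary changes", and the reverse. Section D.4.c (Justification of Sample Size) repeats this: "whether the activity changes are greater in the participants who select exercise as compared to those who selected nutrition or dietary changes and vice versa". Neither section limits the contrast to the concurrent cohort, and neither names a test or an effect size for it.

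Section C.3.f.6 gives two lists of goal categories. The Action Plan Worksheet asks for a goal "in one of 3 categories (activity level/exercise, diet/eating/drinking, or mindfulness meditation practice". The APIS-5 asks patients to classify goals as "diet/eating/drinking, exercise/activity, sleep, medication, reducing substance use, and self-care".

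Section D.3.b.2 plans HEART "for a total of 70 participants (40 alumni, 20 intervention, and 10 waitlist", with a stated minimum of 47 and maximum of 100.

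**The concern.** The hypothesis and the analysis ask different questions. The hypothesis asks whether an activity goal is followed by more activity than the diet, mindfulness and sleep goals. The analysis asks whether it is followed by more activity than a diet goal. Mindfulness practice is one of only two non-activity categories on the Worksheet, so a whole group named in the hypothesis has no place in the planned contrast. Any participants with a sleep goal are left out as well.

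Two things are at stake. A result from the planned contrast could not be reported as a test of hypothesis 8. And a contrast in an already small sample would leave out participants whose data are collected anyway. With both versions standing in the protocol, the comparator could also be chosen after the data are seen.

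**Working it through.** **Step 1. The plan's own HEART power figures.** D.4.c claims 80% power for r = 0.33 with 70 participants and for r = 0.4 with 47, at alpha 0.05. With Fisher's z and a two-sided test, n = ((1.960 + 0.842) / atanh(r))² + 3.

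- r = 0.33: (2.802 / 0.3428)² + 3 = 69.8, so 70. Power at 70 is 80.1%.
- r = 0.40: (2.802 / 0.4236)² + 3 = 46.7, so 47. Power at 47 is 80.2%.

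Both reproduce. They concern correlations and do not depend on the comparator. The plan states no power for the goal-type contrast.

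**Step 2. Comparators side by side.**

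| Place | Compared with activity/exercise goals | Cohort |
|---|---|---|
| A.2.b, hypothesis 8 | diet, mindfulness or sleep goals | concurrent |
| C.5.b | nutrition or diet goals | not restricted |
| D.4.c | nutrition or diet goals | not restricted |

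No section adds the mindfulness or sleep goals back to this contrast.

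**Step 3. Effect on precision.** Let a, d and m be the fractions choosing activity, diet and mindfulness goals on the three-category Worksheet (a + d + m = 1). Assume a common SD.

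- Diet-only comparator: SE = SD × √(1/(Na) + 1/(Nd)).
- Diet plus mindfulness: SE = SD × √(1/(Na) + 1/(N(d + m))).
- The squared ratio of the first to the second simplifies to 1 + am/d.

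The ratio does not depend on N and exceeds 1 for any m above zero. The documents give no split, so these splits are assumptions. Detectable differences are (1.960 + 0.842) × SE in SD units, for 80% power at two-sided 0.05, diet-only first and pooled second.

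| Assumed split a/d/m | 1 + am/d | Diet-only SE larger by | Detectable, N = 70 | Detectable, N = 30 |
|---|---|---|---|---|
| 45/45/10 | 1.10 | 4.9% | 0.71 vs 0.67 | 1.08 vs 1.03 |
| 40/40/20 | 1.20 | 9.5% | 0.75 vs 0.68 | 1.14 vs 1.04 |
| one third each | 1.33 | 15.5% | 0.82 vs 0.71 | 1.25 vs 1.09 |
| 50/25/25 | 1.50 | 22.5% | 0.82 vs 0.67 | 1.25 vs 1.02 |
| 30/20/50 | 1.75 | 32.3% | 0.97 vs 0.73 | 1.48 vs 1.12 |

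For the equal split at N = 70 (23.3 per goal), the SEs are √(2/23.3) = 0.293 SD and √(1/23.3 + 1/46.7) = 0.254 SD. For a true difference of 0.8 SD, the normal approximation gives power of 78.0% against 88.4%. At N = 30, the planned size of the concurrent cohort (20 + 10), it gives 43.2% against 54.2%.

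**The case against.** The strongest reply is that little rests on this contrast. D.4.c declares HEART underpowered for between-group differences and names feasibility and validation as its primary aims. The goal-type comparison comes last, as something also to be examined. This stands, and it sets the severity.

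Four stronger readings are tempting, and the documents do not support them.

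- *This is HEART's only check of goals against tracked behaviour.* It is not. C.5.b also plans the reverse contrast, correlations of the initiation score with the behaviour matching each participant's goal, and the percentage of initiation events with a corresponding behavioural change.
- *Participants with mindfulness goals are dropped from the analysis.* They are absent from this contrast only. Change in mindfulness practice is a listed outcome in the correlations.
- *Diet choosers are the less clean comparator because they may also become more active.* No section says so. The same worry applies to mindfulness goals: the practices described in C.3.e.1 include walking meditation and gentle yoga, and MTPC follows the MBSR structure (C.3.e.4).
- *The loss is a single figure.* A t-test with 23 vs 47 against 23 vs 23 and a 0.7 SD difference gives power of 77% against 64%. That rests on one assumed split, and on 70 participants although hypothesis 8 is headed for the concurrent cohort.

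It can also be argued that hypothesis 8 does not call for pooling, and that exercise versus diet is a coherent symmetric contrast to which the hypothesis could be aligned instead. The first part is fair. But even read as a comparison with each goal, the mindfulness and sleep parts go untested. Narrowing the hypothesis would remove the inconsistency, but would give up a question the collected data can address.

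**Conclusion.** The inconsistency is in the current text. As stated, hypothesis 8's prediction about goal type is not tested by C.5.b or D.4.c, and participants with mindfulness or sleep goals are missing from this contrast.

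The direction of the precision loss holds for any non-zero number of mindfulness choosers, provided SDs are similar. Its size cannot be fixed from the documents: the diet-only SE is 15.5% larger under an equal split and roughly 5% to 32% larger over the splits tried. Pooling estimates the same effect as diet-only only if activity changes similarly in the pooled goal groups. Otherwise the two contrasts are different estimands, and the mismatch in the question matters as much as the precision.

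The consequence is small. This is a secondary, exploratory look in a pilot, and no stated power, sample size or primary aim changes. It is a worthwhile correction, not a threat to HEART.

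**What to change.** In C.5.b and D.4.c:

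- Make the main activity contrast activity goal versus the diet, mindfulness and sleep goals named in hypothesis 8.
- Keep exercise versus diet, and the reverse, as a secondary contrast.
- Show the activity change in each goal group descriptively.
- State whether the contrast uses the concurrent cohort or all HEART participants, and match the heading of hypothesis 8 to that choice.

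In C.3.f.6, reconcile the three Worksheet categories with the six on the APIS-5. The Worksheet has no sleep category although hypothesis 8 names sleep. The APIS-5 lists self-care but not mindfulness practice by name, and adds medication and substance use. Until the lists agree, membership of the comparator is not fixed.

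The cost is a few sentences, with no new data, visits or participants. The one drawback is that a pooled comparator mixes goal types whose activity changes may differ; the separate display by goal makes that visible.
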